### 8.2. Analysis Populations

The full analysis set (FAS) includes all randomized subjects who have received at least 1 dose of each study treatment (OM, moxifloxacin, and placebo).

The PK population will include all subjects who received at least 1 dose of OM and have evaluable PK data. Any subject who experiences emesis within 4 hours of dosing or diarrhea within 24 hours of dosing may be excluded from the PK analysis.

The QT/QTc analysis set will include all subjects in FAS with measurements at baseline as well as on-treatment with at least 1 postdose timepoint with a valid  $\Delta QTcF$  value in Part B. The QT/QTc analysis set will be used for the by-timepoint and categorical analyses of cardiodynamic ECG parameters.

The PK/QTc analysis set will include all subjects who are in both the QT/QTc and PK analysis sets with at least 1 pair of postdose PK and QTcF data from the same timepoint. The PK/QTc analysis set will be used for the concentration-QTc analysis in Part B.

The safety analysis set will include all subjects who receive at least 1 dose of study treatment.

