#### Part B

- Treatment A: Placebo oral solution
- Treatment B: 50-mg OM oral solution
- Treatment C: 400-mg moxifloxacin oral tablet

Approved

After completing Part A, eligible subjects will be randomized to receive 3 treatments in 1 of 6 sequences, as follows:

Sequence	Period 1	Period 2	Period 3
1	A	B	C
2	B	C	A
3	C	A	B
4	A	C	B
5	C	B	A
6	B	A	C

Subjects will be admitted to the research facility on Day -1 of Period 1 in Part B, at which time Check-in procedures will be performed according to the Schedule of Assessments in [Appendix 6](#). After an overnight fast of at least 10 hours, subjects will be administered treatment with 250 mL of water. No food will be allowed for at least 4 hours postdose. Water is allowed as desired except for 1 hour before and after drug administration. Placebo and OM treatments will be double-blinded and moxifloxacin treatment will be open-label. Subjects will receive standardized meals at approximately the same time.

Subjects will stay at the research facility throughout Part B, and study assessments will be performed according to the Schedule of Assessments in [Appendix 6](#), including continuous ECG recording, digital ECG extractions, and PK sample collections to determine plasma OM and moxifloxacin concentrations. Additionally, standard safety assessments, including 12-lead ECGs and vital signs monitoring, will be performed and safety and tolerability monitoring will be conducted throughout the study. Subjects will be discharged after completion of Day 6 activities in Period 3.

All study treatments will be separated by a washout period of at least 7 days (including between Part A and Part B).

The EOS visit will complete a subject's participation in this study after Period 3. If there is a clinically significant clinical or laboratory abnormality that requires monitoring, the subject will be followed until resolution of the abnormality or until it is considered stable. If possible, EOS procedures will be performed on subjects who withdraw early from the study.

The primary completion date is defined as the date when the last subject is assessed or receives an intervention for the final collection of data for the primary endpoint, for the purposes of conducting the primary analysis, whether the study concluded as planned in the protocol or was terminated early. The planned primary completion date is the date when the last subject has completed the assessments on Day 6 of Period 3 in Part B.

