#### **4.7. Discontinuation of Study Treatment**

Subjects (or a legally acceptable representative) can decline to continue receiving investigational product and/or other protocol-required therapies or procedures at any time during the study but continue participation in the study. If this occurs, the Investigator is to discuss with the subject the appropriate processes for discontinuation from investigational product or other protocol-required therapies and must discuss with the subject the possibilities for continuation of the Schedule of Assessments ([Appendix 6](#)) including different options of Follow-up (eg, in person, by phone/mail, through family/friends, in correspondence/communication with other treating physicians, from the review of medical records) and collection of data, including endpoints, adverse events, and must document this decision in the subject's medical records. Subjects who have discontinued investigational product and/or other protocol-required therapies or procedures should not be automatically removed from the study. Whenever safe and feasible, it is imperative that subjects remain on study to ensure safety surveillance and/or collection of outcome data.

Approved

Reasons for removal from protocol-required investigational product(s) or procedural assessments include any of the following:

- Decision by the Sponsor
- Lost to Follow-up
- Death
- Protocol deviation
- Noncompliance
- Adverse events
- Subject request
- Pregnancy

In addition, a subject must be discontinued from study treatment if either of the following occur:

- QTcF > 500 ms (as confirmed by 2 ECGs taken within 1 hour)
- Increase in QTcF > 60 ms compared to predose baseline.

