### **7.2.2. Safety 12-Lead Electrocardiogram**

Standard safety 12-lead ECGs will be recorded at the times indicated in the Schedule of Assessments in [Appendix 6](#) in each treatment period after the subject has been supine or semi-recumbent and at rest for at least 5 minutes to detect any immediate ECG effects for subject safety. These ECGs will be viewed by the Investigator locally, with the Investigator only blinded to OM or placebo treatment.

Any on-therapy ECG with a QTcF > 500 ms (as defined by automatically measured intervals) should be confirmed by a second ECG taken within 1 hour. If the second safety ECG confirms a QTcF > 500 ms, the subject should be discontinued from the study.

Additional 12-lead ECGs may be performed at other times if judged to be clinically appropriate or if the ongoing review of the data suggests that a more detailed assessment of ECGs is required.

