## 5.2 Analysis Populations

The analysis populations for cardiodynamic ECG assessment are defined as follows (Table 1).

Table 1 Analysis sets for cardiodynamic ECG assessment in Part B

Population	Definition
Full analysis set (FAS)	All randomized subjects who have received at least 1 dose of each study treatment (OM, moxifloxacin, and placebo).
PK analysis set	All subjects who received at least 1 dose of OM and have evaluable PK data. Any subject who experiences emesis within 4 hours of dosing or diarrhea within 24 hours of dosing may be excluded from the PK analysis.

Population	Definition
QT/QTc analysis set	All subjects in FAS with measurements at baseline as well as ontreatment with at least 1 postdose time point with a valid $\Delta QTcF$ value. The QT/QTc analysis set will be used for the by-time point and categorical analyses of cardiodynamic ECG parameters.
PK/QTc analysis set	All subjects who are in both the QT/QTc and PK analysis sets with at least 1 pair of postdose PK and QTcF data from the same time point as well as subjects in the QT/QTc analysis set who received placebo. The PK/QTc analysis set will be used for the concentration-QTc analysis in Part B.

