# 6 Analysis

## 6.1 By-Time Point Analysis (Primary Analysis)

The primary analysis of the QT/QTc data will be the "by-time point" analysis for QTcF, based on a linear mixed-effects model with  $\Delta$ QTcF as the dependent variable; period, sequence, time (categorical), treatment (OM, moxifloxacin, and placebo), and time-by-treatment interaction as fixed effects; and baseline QTcF as a covariate. An unstructured covariance matrix will be specified for the repeated measures at time points for subject within treatment period. If the model with an unstructured covariance matrix fails to converge, other covariance matrices such as compound symmetry and autoregressive will be considered. The model will also include a subject-specific random effect. If the fixed effects for period and/or sequence should prove to be not significant (i.e., if the P value > 0.1), these effects may be

removed from the model and the analysis will be repeated without those covariates. From this analysis, the least squares (LS) mean, SE, and 2-sided 90% CI will be calculated for the contrast "OM versus placebo" at each postdose time point, separately. If the upper bound of the CI of  $\Delta\Delta$ QTcF lies below 10 ms for all postdose time points, OM will be concluded not to have a significant effect on QT interval prolongation.

The SAS code for the by-time point analysis for QTcF is as follows.

PROC MIXED DATA=ECG; CLASS SUBJID TREAT TIME PERIOD SEQUENCE; MODEL DQTC=BASE TREAT TIME TREAT\*TIME PERIOD SEQUENCE/DDFM=KR; random intercept / SUBJECT = SUBJID type=UN; REPEATED TIME / SUBJECT = PERIOD\*SUBJID type = un; LSMEANS TREAT\*TIME/CL DIFF ALPHA=0.1; RUN;

Where ECG=QT/QTc analysis set, SUBJID=subject identifier, TREAT=treatment (OM, moxifloxacin, and placebo), TIME=nominal time point, BASE= baseline QTcF, PERIOD=period, SEQUENCE=sequence, and DQTC=ΔQTcF.

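### The QT analysis sets admit only subjects dosed with all three treatments, so a subject stopped for QTc prolongation after OM in Period 1 or 2 leaves the primary, core-lab categorical and concentration-QTc analyses

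*Protocol*

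**What the plan says.** Protocol 8.2 defines the full analysis set (FAS) as "all randomized subjects who have received at least 1 dose of each study treatment (OM, moxifloxacin, and placebo"), and SAP 5.2, Table 1, repeats the rule. The QT/QTc set consists of FAS members with a baseline and at least one valid postdose change in QTcF. Protocol 8.2 gives its use: "The QT/QTc analysis set will be used for the by-timepoint and categorical analyses of cardiodynamic ECG parameters". SAP 5.2 agrees, and the note under the primary model code in SAP 6.1 reads "Where ECG=QT/QTc analysis set". The PK/QTc set, used for the concentration-QTc analysis, is nested again: "All subjects who are in both the QT/QTc and PK analysis sets". The placebo clause that the SAP adds is also confined to the QT/QTc set.

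Protocol 4.7 says that "a subject must be discontinued from study treatment if either of the following occur": a confirmed QTcF above 500 ms, or a rise above 60 ms from predose baseline. Protocol 5 defines study treatment to include placebo and the non-investigational product, so no later period is dosed after such a stop. Under Protocol 3.1, Part B, "eligible subjects will be randomized to receive 3 treatments in 1 of 6 sequences".

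Neither document makes an exception for stopped subjects or lists an analysis on a wider set.

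**The concern.** The study is meant to exclude an effect: OM passes if the upper 90% bound lies below 10 ms at every postdose timepoint. Entry to that analysis depends on completing all three treatments, and completing them depends in part on not having a long QTcF. For stops triggered by OM, the subjects removed are those with the largest apparent effect, which tends to favour passing. The same subject is absent from the core-lab table that counts values above 500 ms and rises above 60 ms, where such an event should appear.

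There is also a loss unrelated to QTc. In sequences 1 and 6 moxifloxacin comes last. Anyone who leaves after Period 2 has complete OM and placebo periods, yet is dropped from the OM comparison for lack of the positive control.

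**Working it through.** **The plan's own figure.** Inputs from Protocol 8.1: 48 evaluable subjects, within-subject SD 7 ms, true difference 3 ms, margin 10 ms, one-sided 5%, 8 timepoints.
- SE = 7 × √(2/48) = 1.429 ms, and (10 − 3)/1.429 = 4.90.
- Power per timepoint = Φ(4.90 − 1.645) = 0.9994. Over 8 independent timepoints, 0.9994⁸ gives 0.995 before rounding, against 99.5% stated.
- With SD 8 ms the result is 0.967, against 96.5% stated.

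The sample size is not in question.

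**Who is removed.** A = placebo, B = OM, C = moxifloxacin.

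| Sequence | Order | OM period | Not received after a stop on OM | In FAS |
|---|---|---|---|---|
| 1 | A B C | 2 | moxifloxacin | no |
| 2 | B C A | 1 | moxifloxacin, placebo | no |
| 3 | C A B | 3 | none | yes |
| 4 | A C B | 3 | none | yes |
| 5 | C B A | 2 | placebo | no |
| 6 | B A C | 1 | placebo, moxifloxacin | no |

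Four of six sequences are affected, or 40 of 60 subjects at 10 per sequence. If one OM-triggered stop is equally likely in any sequence, the chance of removal is 40/60 = 67%. With two such stops, the chance that at least one is removed is 1 − (20×19)/(60×59) = 89%. Counting the 25-mg Part A dose as OM does not help, because placebo or moxifloxacin is still missing.

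**Effect on the upper bound (assumed values).** Take 48 retained subjects with mean difference 3 ms and SD of the difference 7√2 = 9.90 ms (variance 98). Add back k subjects, each with a placebo-corrected change of d at one timepoint:
- n = 48 + k and m = (48×3 + k·d)/n
- s² = [47×98 + 48(3 − m)² + k(d − m)²]/(n − 1)
- upper bound = m + t(0.95, n − 1) × s/√n

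| k | m, d = 65 | SE, d = 65 | Upper, d = 65 | Upper, d = 40 |
|---|---|---|---|---|
| 0 | 3.00 | 1.429 | 5.40 | 5.40 |
| 1 | 4.27 | 1.887 | 7.43 | 6.42 |
| 2 | 5.48 | 2.212 | 9.19 | 7.36 |
| 3 | 6.65 | 2.462 | 10.77 | 8.23 |

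This paired calculation applies directly only to sequence 1, the one affected sequence in which placebo precedes OM.

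**Affected subjects without placebo data.** Generalised least squares for one timepoint, with a random subject intercept, within-subject SD 7 ms, 48 complete subjects and one added subject at 65 ms on OM, gives these OM-minus-placebo estimates (3.00 with none added):

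| Between-subject SD (assumed, ms) | OM only (sequences 2, 6) | OM and placebo (sequence 1) |
|---|---|---|
| 0 | 4.27 | 4.27 |
| 3.5 | 4.01 | 4.27 |
| 7 | 3.63 | 4.27 |
| 10 | 3.42 | 4.27 |

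Sequence 5 (moxifloxacin, then OM) falls between the two, from 4.27 down to 3.76 ms over the same range.

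**Effect on the categorical table.** One restored subject changes the count from 0/48 to 1/49 (2.0%).

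**The case against.** The strongest reply is that the trigger is remote. On the planning values, a 60 ms rise is (60 − 3)/7 = 8.1 within-subject SDs from the mean. Subjects are healthy, prolonged QTcF at screening is an exclusion, and exposure is screened in Part A. This stands: the number of such stops may well be zero.

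Reversal also needs an extreme case: three subjects, near +65 ms, at the same timepoint, with their own placebo data, so drawn from the 10 in sequence 1. When the model re-estimates its variances, subjects with OM data only are treated largely as high-intercept subjects. A single-timepoint random-intercept simulation under assumed variances put the upper bound with three restored at about 5.7 to 6.4 ms for OM-only subjects, 8.8 to 9.8 ms for sequence 5 and 9.7 to 10.4 ms for sequence 1. This stands too. For stops in Period 1 the wider set would change the primary bound little, although it would still correct the categorical table.

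The stop and the endpoint are not the same measurement. The 500 ms rule uses safety ECGs, "as defined by automatically measured intervals" (Protocol 7.2.2), and the 60 ms rule names no ECG source. The primary value comes from core-lab replicates. A stop is therefore linked to a long core-lab QTcF, but not identical with it.

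The event is not hidden. The subject stays in the safety set, the safety-ECG summaries of Protocol 8.4.5 and the SAP listings. However, none of these feeds the 10 ms decision.

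The direction is not uniform either. Stops on moxifloxacin are removed as well, which works against showing assay sensitivity, and unrelated dropouts have no fixed direction. Some withdrawn subjects may be replaced (Protocol 4.5). These points narrow the claim but do not justify an outcome-related exclusion that the model does not need.

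**Conclusion.** The concern holds. The set definitions remove a subject stopped for QTc prolongation after OM in sequences 1, 2, 5 and 6 from all three QT analyses; sequences 3 and 4 are unaffected. For these stops the exclusion is related to the outcome and tends to favour the study's conclusion.

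The size depends on a stop rate that the documents do not give. In the paired illustration at +65 ms, one or two excluded subjects would not reverse the conclusion and three would; at +40 ms three would not. Subjects without placebo data move the estimate less. This should be corrected, but it does not by itself invalidate the design. The reason to act is that the rule is avoidable: the planned mixed model, with a random subject effect and change from baseline within each period, can use incomplete subjects.

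**What to change.** In Protocol 8.2 and SAP 5.2 (Table 1), define the QT/QTc set as all randomised subjects with at least one Part B dose, a baseline for that period and at least one valid postdose change in QTcF in the same period. Use every qualifying period in the existing mixed model. In the categorical tables, use the number of subjects dosed with each treatment as the denominator. Let the PK/QTc set follow from this definition, and keep the three-treatment set as a sensitivity analysis.

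The concentration-QTc model in SAP 6.3 takes change from baseline with a treatment term, so it can use subjects with no placebo period. The model in Protocol 8.3.5 subtracts each subject's own placebo value and cannot. State that the SAP model applies.

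The cost is wording in two sections, that one clarification and one sensitivity run. No extra data or subjects are needed, the model statement in SAP 6.1 is unchanged, and no stopping rule is touched.

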### 8.3. Statistical Analyses

The statistical analysis plan (SAP) will be developed and finalized before database lock. Below is a summary of the timing and methods for the planned statistical analyses. To preserve study integrity, the final analysis will be conducted and reported following the EOS, as defined in [Section 3.1](#).

### **8.3.1. Primary Analysis**

Primary analysis will be conducted after all subjects have either completed all the scheduled study visits or have early terminated from the study. At that time, the database will be cleaned, processed, and locked. Based on the locked data, cardiodynamic, PK, and safety analyses will be performed.

### **8.3.2. General Considerations**

Summary statistics for continuous variables will include number of subjects, mean, median, SD or standard error, minimum, and maximum. For categorical variables, frequency and percentage will be given.

Safety data will be analyzed and reported by treatment (OM, placebo, or moxifloxacin).

Statistical inferences will be provided for analyses of primary endpoints. Unless specified otherwise, all statistical tests are 2-sided with a significance level of 0.05; no statistical inference and imputation will be conducted for analyses of safety endpoints.

### **8.3.3. Cardiodynamic ECG Assessments**

The Cardiac SAP will provide details on the planned electrocardiography analyses.

#### **8.3.3.1. Baseline for Cardiodynamic ECG Assessments**

For all continuous ECG parameters from each period, baseline will be the average of the measured ECG intervals from the 3 predose timepoints (-1.25, -1, and -0.75 hours) for the respective period.

#### **8.3.3.2. Primary Cardiodynamic Analysis**

The primary analysis of the QT/QTc data will be the “by-timepoint” analysis for QTcF, based on a linear mixed-effects model with  $\Delta$ QTcF as the dependent variable; period, sequence, time (categorical), treatment (OM, moxifloxacin, and placebo), and time-by-treatment interaction as fixed effects; and baseline QTcF as a covariate. An unstructured covariance matrix will be specified for the repeated measures at timepoints for subject within-treatment period. If the model with an unstructured covariance matrix fails to converge, other covariance matrices such as compound symmetry and autoregressive will be considered. The model will also include a subject-specific random effect. If the fixed effects for period and/or sequence should prove to be nonsignificant (ie, if the p-value > 0.1), these effects may be removed from the model and the analysis will be repeated without those covariates. From this analysis, the least squares (LS) mean and 2-sided 90% CI will be calculated for the contrast “OM versus placebo” at each postdose timepoint, separately. If the upper bound of the CI lies below 10 msec for all postdose timepoints, OM will be concluded not to have a significant effect on QT interval prolongation.

#### **8.3.3.3. Secondary Cardiodynamic Analyses**

For HR, PR, and QRS intervals, the analysis will be based on the change-from-baseline post-dosing ( $\Delta$ HR,  $\Delta$ PR, and  $\Delta$ QRS). The same model will be used as described for QTcF in

the by-timepoint analysis. The LS mean, standard error, and 90% CI from the statistical modeling for both change-from-baseline and placebo-corrected change-from-baseline values will be listed in tables and graphically displayed.

#### **8.3.3.4. Assay Sensitivity**

The analysis to show assay sensitivity will be based on the change-from-baseline post-dosing QTcF of moxifloxacin. The same model will be used as described for the primary analysis. For the timepoints 2, 3, and 4 hours after dose administration, the contrast in treatment  $\Delta\Delta\text{QTcF}$  = “moxifloxacin – placebo” will be tested against the 1-sided null hypothesis  $\Delta\Delta\text{QTcF} \leq 5$  msec at the 5% level. Multiplicity will be controlled using the Hochberg procedure. If after this procedure QTc ( $\Delta\Delta\text{QTcF}$ ) is significantly larger than 5 msec for at least 1 timepoint, assay sensitivity will be considered shown. In addition, 2-sided 90% CIs will be obtained for the contrast at all timepoints and used in the figures.

#### **8.3.3.5. Categorical Analyses**

The results for categorical outliers, T-wave morphology, and U-wave presence will be summarized in frequency tables with counts and percentages for both number of subjects and number of timepoints. For categorical outliers, the number (percentage) of subjects as well as timepoints that had increases in absolute QTcF values  $> 450$  and  $\leq 480$  msec,  $> 480$  and  $\leq 500$  msec, or  $> 500$  msec, and changes from predose baseline of  $> 30$  and  $\leq 60$  msec, or  $> 60$  msec; increase in PR from predose baseline  $> 25\%$  to a PR  $> 200$  msec; increase in QRS from predose baseline  $> 25\%$  to a QRS  $> 120$  msec; decrease in HR from predose baseline  $> 25\%$  to a HR  $< 50$  bpm; and increase in HR from predose baseline  $> 25\%$  to a HR  $> 100$  bpm will be determined. For T-wave morphology and U-wave presence, the analyses will be focused on change from baseline (ie, treatment-emergent changes).

Outliers for HR and PR, QRS, QT, and QTc intervals will be summarized. New ECG morphological changes will be summarized. “New” means not present on any baseline ECG and becomes present on at least 1 on-treatment ECG.

#### **8.3.4. Pharmacokinetic Analyses**

The plasma PK parameters of OM will be calculated using standard noncompartmental methods. Plasma concentrations and PK parameters for OM and potentially plasma concentrations for moxifloxacin will be summarized by descriptive statistics. No formal statistical analyses are planned.

The following PK parameters will be calculated whenever possible, based on the plasma concentrations of OM:

$C_{\max}$	maximum observed concentration
$t_{\max}$	time to maximum observed concentration
$AUC_{0-t}$	area under the concentration-time curve from time 0 to the time of the last quantifiable concentration
$AUC_{\text{inf}}$	area under the concentration-time curve from time 0 to infinity

%AUC extrap	percentage of AUC inf that is due to extrapolation
t 1/2	apparent terminal elimination half-life
CL/F	apparent total plasma clearance
V Z /F	apparent volume of distribution

Other PK parameters may also be calculated. Moxifloxacin plasma samples may be assayed and PK parameters will be calculated only if deemed necessary.

